#### **Laboratory data:**

For potassium all central and local labs will be included in the data summary; for other lab assessments, only the central lab assessments will be included in the data summary.

All central and local labs will be included in the data listings.

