## 8.5. Safety Monitoring Rules

Please refer also to the ‘Guidance for Investigator’ section of the Investigator’s Brochure.

For the purposes of Safety Monitoring Baseline is defined as:

- Monitoring Rules for Liver Chemistry Tests – Baseline is defined as the average of Screening and Day 1

In addition to the standard monitoring of clinical safety parameters, the following guidelines are provided for the monitoring of selected parameters chosen based on preclinical and clinical observations.

Confirmation Guidance: At any time during the study (Treatment or Post-Treatment Periods), the initial clinical laboratory results meeting the safety monitoring criteria presented below **must be confirmed** by performing measurements (ideally in the same laboratory that performed the initial measurement) on new specimens. All new specimen collections should take place as soon as possible (ideally within 3 days of the initial collection). For stopping rules, if the initial laboratory result is observed during the Treatment Period, the results from the retest **must be available** prior to administering the next dose of Study Drug (ION-827359 or placebo).

Re-dosing Guidance: Patients with initial laboratory test values that reach a stopping rule must not be re-dosed until the re-test results are available. In general, patients who do not meet the stopping rules based upon retest may continue dosing. However, the Investigator and the Sponsor Medical Monitor (or appropriately qualified designee) should confer as to whether additional close monitoring of the subject is appropriate. If any of the stopping criteria described below (refer to Sections 8.6.1 to 8.6.4 are met, the subject will be permanently discontinued from further treatment with Study Drug (ION-827359 or placebo), evaluated fully as outlined below and in consultation with the Sponsor Medical Monitor or appropriately qualified designee, and will be followed up in accordance with Section 8.8 of the protocol.

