### **3.4.3      Laboratory Measurements**

The list of safety lab analytes collected throughout the study is provided in protocol Appendix B.

All lab data collected will be presented in subject listings.

Results from chemistry, hematology, complements, and coagulation panels as well as the change and percent change from baseline will be summarized by treatment group and study visit using descriptive statistics.

For ALT and AST, the number and percent of subjects falling in each of the following categories based on the confirmed results will be tabulated by treatment group

- ALT/AST > 3 x ULN, which is confirmed
- ALT/AST > 5 x ULN, which is confirmed

For platelet, the number and percentage of subjects falling in each of the following categories based on the confirmed results will be tabulated by treatment group for 100,000/mm^3 to <140,000/mm^3 and <100,000/mm^3.

A confirmed value is based on a consecutive lab value within 7 days. If that value is in the same or worse category the initial value is confirmed. If the consecutive value is in a better category, then the initial value is confirmed using the consecutive value category. If there is no retest within 7 days, then the initial value is presumed confirmed. If there are multiple results on the same day, then the worst value will be utilized in the analysis.

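### On the plain reading of the SAP, a central ALT/AST or platelet abnormality refuted only by a local retest would be tabulated as confirmed

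*Combined protocol and SAP*

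**What the plan says.** SAP section 3.1.1, under Laboratory data, sets the source of results. Potassium is the one exception: "For potassium all central and local labs will be included in the data summary". For everything else, "for other lab assessments, only the central lab assessments will be included in the data summary". Local results are still reported elsewhere: "All central and local labs will be included in the data listings".

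SAP section 3.4.3 tabulates patients by treatment group in confirmed categories. For transaminases these are "ALT/AST > 3 x ULN, which is confirmed" and the matching category above 5 x ULN. For platelets they are 100,000 to below 140,000 and below 100,000 per mm³. The confirmation rule has three parts:

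- The retest: "A confirmed value is based on a consecutive lab value within 7 days".
- A retest that looks better: "If the consecutive value is in a better category, then the initial value is confirmed using the consecutive value category".
- No retest: "If there is no retest within 7 days, then the initial value is presumed confirmed".

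Protocol section 8.5 requires values that meet the monitoring criteria to be repeated, "ideally in the same laboratory that performed the initial measurement) on new specimens". The same laboratory is preferred, not required. Protocol section 8.6.1 also presumes confirmation of liver values, but only where the retest was not done or the value is missing.

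**The concern.** The two SAP rules sit in different sections and neither refers to the other. If local results are removed before the confirmation rule is applied, a local retest that was done looks the same as no retest, and the default then labels the central value confirmed. A patient whose high ALT was repeated locally and found normal would appear in the confirmed-elevation table, although the protocol's own confirmation step had cleared the value.

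For the values at issue the error runs one way: it adds confirmed cases and never removes one. Efficacy is now descriptive only and the groups are small, so readers will look at individual counts in these safety tables.

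**Working it through.** The plan gives no figure for this point, so the check is to apply its rules.

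**Step 1. Could a scheduled central draw supply the retest anyway?** Chemistry and hematology days and visit windows come from protocol Appendix A.

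| Interval | Nominal gap (days) | Shortest gap within windows (days) |
|---|---|---|
| Day 1 to 15 (± 2) | 14 | 13 − 1 = 12 |
| Day 15 to 29 (± 3) | 14 | 26 − 17 = 9 |
| Day 29 to 43 (± 3) | 14 | 40 − 32 = 8 |
| Day 43 to 57 (± 3) | 14 | 54 − 46 = 8 |
| Day 57 to 85 (± 2) | 28 | 83 − 60 = 23 |
| Day 85 to 92 (± 5) | 7 | may overlap; longest is 97 − 83 = 14 |

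Up to Day 85, no scheduled draw falls within 7 days of the one before, even with the windows used in full. Confirmation then depends on an extra sample or an early-termination visit. SAP section 3.1.1 admits unscheduled results to the abnormality summaries, so an extra central sample counts. It does not lift the central-only limit for an extra local one.

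**Step 2. Apply the confirmation rule to constructed ALT sequences (multiples of ULN).** The middle columns show the confirmed category with central records only and with all records. The last column applies the change proposed below.

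| Sequence | Central only | All records | Proposed rule |
|---|---|---|---|
| Central 6 on Day 29, local 1 on Day 31, central 1 on Day 43 | > 5 x ULN | not elevated | not elevated |
| Central 6 on Day 29, central 1 on Day 31 | not elevated | not elevated | not elevated |
| Central 6 on Day 29, local 1 on Day 31, central 1 on Day 34 | not elevated | not elevated | not elevated |
| Central 6 on Day 29, local 6 on Day 31, central 1 on Day 43 | > 5 x ULN | > 5 x ULN | > 5 x ULN |
| Central 6 on Day 85, local 1 on Day 87, central 1 on Day 92 | not elevated | not elevated | not elevated |

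Only the first sequence is misclassified. It needs three things together: a central abnormality, a local retest in a better category within 7 days, and no central retest in that time. The same logic applies to platelets, with low counts in place of high values.

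**Step 3. Compare with the protocol.** In the first sequence the retest was done and reported. It is neither omitted nor missing, so the presumption in protocol section 8.6.1 would not apply. That section governs liver values. Section 8.6.3 on platelets asks for confirmation and states no presumption.

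**Step 4. Weight of one patient.** SAP section 1.1 gives 59 dosed. With 2:2:1:1 allocation and the placebo groups pooled (protocol section 10.6), the three groups are in the ratio 2:2:2, so 59 / 3 = 19.7, or about 20 each. One patient is 1 / 20 = 5 percentage points of a group, and 1 / 59 = 1.7 points of all dosed. The actual split is not given, so an even split is assumed. The 5 points describe what one patient weighs. They do not estimate how many patients are affected.

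**The case against.** The strongest reply is that section 3.4.3 is the specific rule, speaks only of a consecutive laboratory value, and names no laboratory. A programmer could take a local retest as that value. This stands as far as it goes: the SAP can be read both ways. But section 3.1.1 is explicit about what enters a summary, and nothing in section 3.4.3 exempts the confirmed tables.

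The second reply is that the situation may be rare. The protocol prefers the laboratory that made the first measurement, SAP section 2.5.2.3 routes site samples to the central vendor, and protocol section 8.5.2 calls for weekly counts once platelets reach 100,000 or less. All of these make a central retest within 7 days more likely. This also stands.

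Third, central-only summaries avoid mixing assays and reference ranges, and presuming confirmation when there is truly no retest is conservative. Neither choice is disputed here.

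A reader might infer more than the documents support:

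- **That local retests must have been common because the result was needed before the next weekly dose.** Protocol section 8.5 ties that requirement to the stopping rules. Many values in these tables, such as platelets from 100,000 to below 140,000, fall outside them.
- **That local results are discarded and local-only abnormalities lost.** They stay in the listings, and a clinically significant one may also be reported as an adverse event. It is true that a purely local abnormality would not enter the confirmed table, but counting it as a new case would mix laboratories. That is a debatable trade-off, not an error.
- **That the potassium exception shows the central-only rule to be wrong elsewhere.** It shows only that the SAP can accommodate local results.

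**Conclusion.** The point holds as a minor gap in the SAP. Under the plain reading of sections 3.1.1 and 3.4.3, a central ALT/AST or platelet abnormality refuted only by a local retest within 7 days would be counted as confirmed, which conflicts with the confirmation step that the protocol allows.

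This rests on two assumptions: that the central-only rule governs the confirmed tables, and that at least one local retest of this kind exists. The documents settle neither, so it cannot be said that any value was misclassified, and the likelihood and size are unknown.

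**What to change.** In SAP section 3.4.3, add that for the confirmed ALT/AST and platelet tables:

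- a local result within 7 days serves as the retest when there is no central retest in that time, with ALT/AST taken as multiples of the local ULN and platelets as counts;
- confirmation is presumed only when neither laboratory has a retest within 7 days.

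A central retest therefore takes precedence where both exist. A local result can confirm or refute a central value but does not create a new case. By-visit summaries stay central only, and local-only abnormalities appear in the listings as now. The change affects tabulation only and leaves the protocol's management and stopping rules untouched.

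The cost is a sentence or two, a small programming change, and local reference ranges for the few local ALT/AST retests. The documents do not say that these ranges were collected. The SAP is dated 26 August 2021, after treatment ended on 29 April 2021, so some may have to be requested from sites. Platelet counts need no conversion.

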#### **3.1.2 Subject Population Analyzed**

Full Analysis Set (FAS): all randomized patients who received at least 1 dose of Study Drug (ION-827359 or placebo) and who have at least 1 post-Baseline efficacy assessment (i.e., post-Baseline FEV1 assessment, E-RS score, CAT score, or SGRQ-C score).

Safety Set: All patients who are randomized and receive at least 1 dose of Study Drug.

PK Population: All subjects who are randomized and receive at least 1 dose of active Study Drug (ION-827359) and have at least 1 evaluable PK sample collected and analyzed with reportable result. This population will be used for PK analyses.

In addition to the above analysis populations, it is recognized that some data displays will be provided for “All Screened”, “Screening Failures” and “All Randomized” subjects but no data analysis will be executed in these populations except for the disposition table that includes all screened subjects.

The Per-Protocol Set (PPS), FAS - Bronchoscopy Subgroup, PPS - Bronchoscopy Subgroup, FAS-HRCT and PPS-HRCT subgroups are defined in the protocol but have been removed from this SAP.

### 3.1.3 Sample Size Consideration

The sample size assumptions for the primary endpoint include:

- The increase in FEV1 from Baseline to the primary time point in the ION-827359 treatment group is 100 mL; no change in the placebo group
- Standard deviation of change in FEV1 is 220 mL
- Significance level (alpha) of 0.05 (2-sided test)

With the above assumptions, a sample size of 174 patients (58 patients in each ION-827359 treatment groups and 29 patients in each placebo group) will provide a power of at least 80% for the primary comparison (pooled ION-827359 treatment groups vs. pooled placebo groups).

Approximately 180 patients will be enrolled in this trial to account for a 3% dropout rate.

### 3.1.4 Planned Interim Analysis

No interim analysis is planned for this study.

### 3.1.5 Incomplete or Missing Data

For EXACT daily diary, if no more than three items are missing, and no more than two of items 9–11 are missing, the missing items will be imputed using the mean of the remaining answered items, rounded to the nearest integer and capped at the maximum score available for that item. Otherwise, the E-RS score will be considered missing for the day.

For CAT questionnaire, if the score is missing for only one item, the missing value will be imputed by the mean value of the remaining seven items. If two or more items are missing, then the CAT score will be considered missing for the visit.

For SGRQ-C questionnaire Part 1, missed items are treated as if the answer was in the negative. A maximum of one missed item is permitted for this section.

For SGRQ-C questionnaire Part 2, items in questions 9, 10, 11, 12, 13 all require a response of either 'True' or 'False'. If neither box is ticked, the item should be coded as missing. The weight for that item should then be removed from the total possible for that component (and the total score). A maximum of 3 missed items for the Activity component (items in questions 9 and 12) and a maximum of 5 items for the Impacts component (items in questions 8, 10, 11, 13, 14) are permitted.

## 3.2 Demographic and Baseline Characteristics and Patient Disposition

Baseline and demographic variables will be summarized descriptively by treatment group and for each analysis population.

Demographic and baseline characteristics to be presented include age, age category (<18, 18 to 64, ≥65 years), gender, race, ethnicity, height, weight, BMI, , percent predicted DLCO, , baseline spirometry assessments, E-RS scores, CAT scores, SGRQ scores, sputum mucins, FRC and RV.

For race summary, if multiple races are recorded in database, 'Multiple Race' will be used in the summary table but details records in the listing.

A separate table will be created for the targeted medical history and smoking history, and will include duration since diagnosis of COPD, COPD exacerbations that required hospitalization in the last year (yes/no), number of hospitalizations for COPD exacerbations in the last year, COPD exacerbations that required oral corticosteroids and/or antibiotic in the last year (yes/no), number of COPD exacerbations in the last year that required oral corticosteroids and/or antibiotics, diagnosis with asthma (yes/no), diagnosis with coronary artery disease (yes/no), diagnosis of congestive heart failure (yes/no), ever used tobacco cigarettes (yes/no), number of packs tobacco per day and number of years smoking.

The duration since diagnosis of COPD will be calculated as the difference between informed consent date and COPD diagnosis date plus 1 day then divided by 365.25. The partial COPD dates will be imputed using the following rules:

- If both month and day are missing then assign July 1st
- If only day is missing then assign 15th

Other medical history data will be provided in the data listing and summarized using MedDRA SOC and preferred term.

Subject enrollment and disposition will be summarized by treatment group. The summary will include: the number of subjects screened, the number of screen failures, the reason for screen failure, the number of subjects randomized, the number and percentage of subjects dosed, the number and percentage of subjects in each analysis population, the number and percentage of subjects in each subgroup, the number and percentage of subjects completing treatment, the primary reason for terminating treatment, the number of subjects completing post-treatment follow-up, and the primary reason for terminating post-treatment follow-up. The percentages will be calculated based on the number of patients randomized.

### **3.3 Efficacy Analyses**

All efficacy analyses will be performed on the FAS. Due to the fact that study treatment terminated after only 60 patients have been randomized, 59 patients have been dosed, and 10 patients have completed the Week 14, all analyses will be descriptive. The model-based analyses described in the protocol will not be conducted.

#### **3.3.1 Change from Baseline in FEV1 at the Primary Time Point**

The FEV1 and other spirometry assessments, as well as change and percent change from baseline to the primary time point, end of treatment period, and other study visits will be summarized by treatment group using descriptive statistics.

At each time point, 3 technically acceptable measurements will be made and recorded. The best readings from each time point for each assessment will be used for analysis.

In addition to the descriptive summary, the proportion of patients who have a greater than 20% reduction in FEV1 post treatment and the proportion of doses that resulted in a greater than 20% reduction in FEV1 will be tabulated by treatment group.

### 3.3.2 Analysis of Secondary Endpoints

#### 3.3.2.1 Change from Baseline in E-RS Total and Subscale Scores at the Primary Time Point

The E-RS assesses respiratory symptoms using the following 11 respiratory symptom items from the EXACT.

The response for each item will be scored according to the E-RS User Manual Version 3.0 as below:

E-RS™ Individual Items	Response	Score
1. Chest congested	Not at all	0
	Slightly	1
	Moderately	2
	Severely	3
	Extremely	4
2. Cough	Not at all	0
	Rarely	1
	Occasionally	2
	Frequently	3
	Almost constantly	4
3. Mucus/phlegm	Not at all	0
	A little	1
	Some	1
	A great deal	2
	A very great deal	3

E-RST™ Individual Items	Response	Score
4. Difficulty bring up mucus	Not at all	0
	Slightly	1
	Moderately	2
	Quite a bit	3
	Extremely	4
5. Chest discomfort	Not at all	0
	Slight	1
	Moderate	2
	Severe	3
	Extreme	4
6. Tight chest	Not at all	0
	Slightly	1
	Moderately	2
	Severely	3
	Extremely	4
7. Breathlessness	Not at all	0
	Slightly	1
	Moderately	2
	Severely	3
	Extremely	4
8. Describe breathlessness	Unaware of breathlessness	0
	Breathlessness during strenuous activity	1
	Breathlessness during light activity	2
	Breathlessness when washing or dressing	3
	Present when resting	3
9. Short of breath personal activities	Not at all	0
	Slightly	1
	Moderately	2
	Severely	3
	Extremely	3
	Too breathlessness to do these	4

E-RST™ Individual Items	Response	Score
10. Short of breath indoor activities	Not at all	0
	Slightly	1
	Moderately	2
	Severely	3
	Extremely	3
	Too breathlessness to do these	3
11. Short of breath outdoor activities	Not at all	0
	Slightly	1
	Moderately	2
	Severely	3
	Extremely	3
	Too breathlessness to do these	3

Patients' daily E-RS total scores will be computed by summing across responses to the 11 items, the score ranges from 0 to 40. The same summation procedure will be used for obtaining the three subscale scores: E-RS Breathlessness is the sum of items 7, 8, 9, 10 and 11, the score ranges from 0 to 17; E-RS Cough & Sputum is the sum of items 2, 3, 4, the score ranges from 0 to 11; and E-RS Chest is the sum of items 1, 5, 6, and score ranges from 0 to 12. The higher scores indicate more severe respiratory symptoms.

Missing EXACT items will be imputed using the rules described in Section 3.1.5 in this SAP. The data will be mapped to study week based on the visit window specified in section 3.1.1. The data in the visit window will be averaged. If patients complete less than 4 daily assessments in a week, then the E-RS scores will be considered as missing for the week.

The change from baseline in the E-RS total and the 3 subscale scores to primary time point and over time as well as change from baseline to the end of treatment period will be summarized by treatment group using descriptive statistics.

### 3.3.2.2 Change from Baseline in CAT at Week 14

The CAT contains eight items: cough, phlegm, chest tightness, breathlessness, limited activities, confidence leaving home, sleeplessness and energy. Each item is presented as a semantic 6-point differential scale from 0 to 5. The total CAT score ranges from 0–40. Higher scores indicate a more severe impact of COPD on a patient's life.

If the score is missing for only one item, the missing value will be imputed by the mean value of the remaining seven items. If two or more items are missing, then the CAT score will be considered missing for the visit.

The change from baseline in the CAT score at Week 14 and other study visits as well as change from baseline to the end of treatment period will be summarized by treatment group using descriptive statistics.

### 3.3.2.3 Change from Baseline in SGRQ at Week 14

The SGRQ is a patient completed, disease-specific instrument designed to measure impact on overall health, daily life, and perceived well-being in patients with obstructive airways disease and includes 50 items addressing three domains of HRQL (symptoms, activity limitations, and impact of the disease on daily life). Recall periods in the questionnaire include the past 4 weeks and the present.

This study will utilize the shorter 40-item version (SGRQ-C) which does not specify a Recall Period. A five-point scale is used for rating the symptoms, and a true/false binary scale is used for activity limitations. Items are assigned a weight according to the degree of distress in the calculation of the overall score as below:

#### **Part 1:**

##### **Question 1: I cough:**

Most days 80.6  
Several days 46.3  
With chest infections 28.1  
Not at all 0.0

##### **Question 2: I bring up phlegm (sputum):**

Most days 76.8  
Several days 47.0  
With chest infections 30.2  
Not at all 0.0

##### **Question 3: I have shortness of breath:**

Most days 87.2  
Several days 50.3  
Not at all 0.0

##### **Question 4: I have attacks of wheezing:**

Most days 86.2  
Several days 71.0  
A few days 45.6  
With chest infection 36.4  
Not at all 0.0

##### **Question 5: How many attacks of chest trouble have you had**

3 or more 80.1  
1 or 2 attacks 52.3  
None 0.0

